2.3 POTENTIAL RISKS AND BENEFITS

2.3.1 POTENTIAL RISKS

Naltrexone for extended-release injectable suspension (XR-NTX; Vivitrol) is FDA-indicated for the treatment of alcohol dependence, so participants in this study may have direct benefit from this treatment. XR-NTX is not a controlled substance.

Sublingual buprenorphine (SL-BUP) is FDA-indicated for the treatment of opioid dependence. SL-BUP is a Schedule III narcotic under the Controlled Substances Act. The use of SL-BUP in a non-opioid dependent population has a risk of misuse or abuse. Buprenorphine is a partial agonist at the mu-opioid receptor and chronic administration produces physical dependence of the opioid type, characterized by withdrawal signs and symptoms upon abrupt discontinuation or rapid taper. The withdrawal syndrome is typically milder than seen with full agonists and may be delayed in onset. However, to mitigate the potential for misuse, dependency, and withdrawal, buprenorphine can be combined with XR-NTX, a medication that blocks the mu receptor involved in psychogenic properties of buprenorphine.

XR-NTX can antagonize the effects of opioids via competitive inhibition of opioid receptors, which raises the concern that the combination of SL-BUP and XR-NTX will make SL-BUP less effective. This would be a risk for individuals who are using opiates or SL-BUP on a regular basis prior to starting XR-NTX, (i.e., the addition of XR-NTX may precipitate opioid withdrawal symptoms). For this reason, this study excludes patients who have recent opioid use or opioid use disorders, and opiates are not allowed to be concurrently taken during the study. XR-NTX is contraindicated in patients receiving opioid analgesics and in patients with current physiologic opioid dependence, acute opiate withdrawal, acute hepatitis or liver failure, and previous hypersensitivity reaction to XR-NTX. Patients with these contraindications are not eligible to participate in this study.

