The CURB study¹⁶ evaluated low dose and high dose SL-BUP added to XR-NTX in participants recovering from current cocaine use disorder and past year (not recent) opioid use or dependence and whom did not necessarily have a diagnosis of PTSD. In the publication of its results, Ling et al (2016) provide an extensive table of the reported and related adverse events, with a breakdown of causal relationship and type of adverse events comparing placebo, low dose and high dose SL-BUP added to XR-NTX. The study found no significant differences in numbers of adverse events or serious adverse events by treatment arm and there were no significant adverse events related to induction onto XR-NTX. None of the serious adverse events were deemed by the medical monitor as study-related¹⁶.

In the current study, XR-NTX is administered as a long-acting injectable, the protective pharmacologic properties are present for the full duration of treatment with SL-BUP, thereby eliminating the risk that the participant will become psychologically or physically addicted to SL-BUP. In addition, we are using low dose SL-BUP (Note: the dose is lower than 16mg dose used in CURB study). At the end of the study XR-NTX is gradually eliminated from the body. Thus, a pharmacologic taper is not needed for either XR-NTX or SL-BUP. Participants should not experience withdrawal symptoms, but to be conservative, they are followed by the investigators for an additional two weeks to monitor the participants for any adverse events related to discontinuation. To be cautious and thorough, the investigators assess for signs and symptoms of opioid withdrawal at the end of the study.

The study uses low dose of buprenorphine (2mg daily) which is usually the target of a taper when stopping treatment in a patient on medication-assisted therapy for opioid use disorders. Withdrawal is highly unlikely with these low doses after 12 weeks of treatment, especially when used in combination with naltrexone. The potential for withdrawal is mitigated by naltrexone. Withdrawal from low dose buprenorphine in patients with non-opioid use disorders is not described in the literature. Case reports of discontinuation of higher dose (12mg to 20 mg daily) buprenorphine indicate that mild opiate withdrawal symptoms last 1 to 2 days and did not require opioid medication or other medication. Psychosocial intervention is recommended, and the lengthy withdrawal regimens might prolong withdrawal symptoms unnecessarily.

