The investigators have designed the study to include two weeks (from Week 12 to Week 14) to monitor the patient for drug discontinuation or withdrawal symptoms. The investigators will treat emergent psychological symptoms with psychosocial support and physical symptoms with the appropriate treatments, such as metoclopramide for nausea, NSAIDs for pain, clonidine for opioid-like withdrawal symptoms, and loperamide for diarrhea. Three to five days after Week 12 discontinuation of medication, the research nurse will call participant to check on emergent adverse symptoms

A caution that is included in the informed consent stating that in a situation when analgesia may be required in a patient who has received full blocking doses of XR-NTX, consideration should be given to regional analgesia, conscious sedation with a benzodiazepine, use of non-opioid analgesics, or general anesthesia. If opioid analgesia is required, the amount of opioid needed may be greater than usual, and the resulting respiratory depression may be deeper and more prolonged. In this case, a rapidly acting opioid analgesic that minimizes the duration of respiratory depression is preferred. XR-NTX can also diminish the benefit from opioid-containing cough, cold, and antidiarrheal preparations, which is listed as a warning in the informed consent. These warning are standard when treating patients with XR-NTX.

Side effects of XR-NTX that led to more discontinuation of treatment compared to placebo include the following: pain, tenderness, induration or pruritus at the site of the injection (3%), nausea (2%), headache (1%), and suicide-related events (0.3%). Other known non-serious side effects that differ from placebo include nausea (29% vs 11%), vomiting (12% vs 6%), diarrhea (13% vs 10%), abdominal pain (11% vs 8%), injection site reactions (65% vs 50%), arthralgia/arthritis (9% vs 5%), muscle cramps (5% vs 1%), rash (6% vs 4%), headache (21% vs

18%) dizziness (13% vs 4%), somnolence/sedation (5% vs 1%), and appetite decrease (11% vs 3%). XR-NTX has the capacity to cause hepatocellular injury when given in excessive doses (the margin of separation between the apparently safe dose of naltrexone and the dose causing hepatic injury appears to be five-fold. XR-NTX does not appear to be a hepatotoxin at the recommended doses used in this study.

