
Adverse events most commonly observed during clinical trials and post-marketing experience for SL-BUP compared to placebo are headache (29% vs 22%), nausea (14% vs 11%), vomiting, hyperhidrosis, constipation (8% vs 3%), signs and symptoms of withdrawal (18% vs 37%, i.e.,

greater in placebo group), insomnia (21% vs 16%), and pain (18% vs 19%). The dose used in this study is lower and may yield fewer side effects.

Although the virtual reality exposure may evoke physiologic reactivity (increased heart rate and skin conductance; alcohol craving), it is not at the level of overt PTSD symptom provocation. The psychophysiological studies* are well tolerated. This protocol has been utilized in previously published studies in both active service member and veteran populations. The virtual reality environments have been reported by military personnel, past and present, as capable of evoking trauma-related memories and physiological responses but not to be re-traumatizing.

*Psychophysiological assessments are optional so as to not be a barrier to enrollment or randomization.

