7.3.5 FINAL STUDY VISITS

At Week 12, the study medication is discontinued, and all Week 12 assessments are completed. At Week 12, the participant is referred back to his/her previous or newly assigned long-term PTSD provider for follow-up and continued treatment. At Week 14, the participant is assessed for discontinuation or withdrawal side effects and resolution or emergence of adverse events. The participant's ongoing clinical treatment plan is confirmed.

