7.3.7 COVID-19 SAFETY PRECAUTIONS

COVID-19 Safety Precautions:

1. Adhere to local VA or University policies or mandates, for example:
 - a. Screening before entering the facility, which may include a 'no touch' method to check temperature and COVID-19 screening questions.
 - b. Participants encouraged or required to wear facial covering/mask while in the buildings, as mandated by the facility.
 - c. Anyone who screens positive for COVID-19 (exposure or symptoms) and/or has a fever will be rescheduled (and possibly tested for COVID-19 as deemed clinically appropriate).
2. Study staff:
 - a. The research team will monitor scheduling of participants in order to allow for social distancing and cleaning procedures between participant visits.
 - b. Research staff members will sanitize high-touch surfaces before and after each in-person visit with disinfectant wipes or sprays.
 - c. Staff members will adhere to local policies regarding wearing protective facial masks, frequent handwashing/use of alcohol-based hand sanitizer, and social distancing.
 - d. Visits will take place in a large enough space so that study staff and the participant can practice social distancing.
 - e. As much as possible, self-assessment forms should be completed via telehealth or phone; and can be given directly to or mailed to the participant in advance of any appointment.
 - f. If the patient desires to complete in-person visit forms on site, staff will honor that request, but maintain social distancing.
 - g. Participants will receive compensation for visits. As needed, study staff will verify their current address in order to be able to mail compensation to the participant.
3. In-Person visits:
 - a. The in-person research visits will be restricted to those that are clinically essential (screening, baseline, Week 4, Week 8, Week 12, and Week 14; due to required labs and/or medication injections).
4. Telehealth/Phone visits:
 - a. Week 1, 2, 6, & 10 visits may be conducted over the phone or telehealth to limit the participants contact (study staff and time in the clinic).
5. Week 14 Visit:
 - a. Week 14 is highly preferred to be conducted in-person or by telehealth due to need for safety check and treatment planning (not as easy to assess over phone without video component).
 - b. At this visit, participant has been off study medications for 2 weeks. Investigators would like to visually assess participants for withdrawal symptoms.

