8.3 ADVERSE EVENT ASSESSMENT AND FOLLOW-UP

AEs are collected from time of first dose taken after randomization through Week 14 follow-up visit. Study investigators follow all SAEs clinically until resolved or clinically stable. The occurrence of an AE or SAE may come to the attention of study personnel during study visits and interviews of a study participant presenting for medical care, or upon review by a study monitor. At each study visit, the LSI or trained designee asks the participant about the occurrence of AE/SAEs since the last visit. All AEs are captured on the appropriate CRF.

Information to be collected includes event description, time of onset, clinician's assessment of severity, relationship to study product (assessed only by those with the training and authority to make a diagnosis), and time of resolution/stabilization of the event. All AEs occurring while on study must be documented appropriately regardless of relationship.

Any medical condition that is present at the time that the participant is screened is considered as a baseline condition and not reported as an AE. However, if the study participant's condition deteriorates at any time during the study, it is recorded as an AE.

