with SL-BUP. SL-BUP should be used with caution in patients with compromised respiratory function (e.g., chronic obstructive pulmonary disease, cor pulmonale, decreased respiratory reserve, hypoxia, hypercapnia, or pre-existing respiratory depression). Cases of cytolytic hepatitis and hepatitis with jaundice have been observed in individuals receiving buprenorphine in clinical trials and through post-marketing adverse event reports. For this reason, patients with severe liver disease or liver failure are excluded, and liver enzymes are measured at baseline and endpoint. SL-BUP may impair the mental or physical abilities required for the performance of potentially dangerous tasks such as driving a car or operating machinery, especially during treatment induction and dose adjustment. Patients should be cautioned about driving or operating hazardous machinery until they are reasonably certain that buprenorphine therapy does not adversely affect his or her ability to engage in such activities. SL-BUP is metabolized to norbuprenorphine primarily by cytochrome CYP3A4; therefore, potential interactions may occur when SL-BUP sublingual tablet is given concurrently with agents that affect CYP3A4 activity. The concomitant use of SL-BUP sublingual tablet with CYP3A4 inhibitors (e.g., azole antifungals such as ketoconazole, macrolide antibiotics such as erythromycin, and HIV protease inhibitors) should be monitored and may require dose-reduction of one or both agents.

The LSI or designee instruct participants (in the consent form and verbally) to immediately report any adverse experiences that may arise and/or any changes in concurrent medications, whether prescription, over-the-counter medications, or herbal supplements.

In the unlikely event that a participant experiences a medical emergency, the local site has access to a medical Center that is fully prepared to respond to any medical event that may arise. Physicians and nurses are fully trained to respond to all types of medical and psychiatric emergencies. A fully equipped crash cart is available near the research clinic.

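### Weeks 12 to 14 are set aside to watch for withdrawal, but no planned by-arm summary isolates post-stop events, and the early-exit rules disagree on whether COWS is done

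*Protocol*

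**What the plan says.** **Why there is a monitoring period.** Protocol 2.3.1 says that chronic buprenorphine produces opioid-type physical dependence and that withdrawal "may be delayed in onset". It judges withdrawal highly unlikely at 2 mg with naltrexone and finds no description of it at low dose in people without opioid use disorder. It cites case reports at 12 to 20 mg in which "mild opiate withdrawal symptoms last 1 to 2 days and did not require opioid medication or other medication". It reserves Weeks 12 to 14 for monitoring.

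**When withdrawal is looked for.** Section 7.3.5: "At Week 12, the study medication is discontinued, and all Week 12 assessments are completed". Section 7.3.7, on Week 14: "At this visit, participant has been off study medications for 2 weeks". The schedule in 7.3.1 marks COWS at screening, Week 12 and Week 14 only. Between the last two, 2.3.1 provides: "Three to five days after Week 12 discontinuation of medication, the research nurse will call participant to check on emergent adverse symptoms". Section 8.3 collects adverse events from first dose to Week 14: "Information to be collected includes event description, time of onset". Section 8.7 tells participants to "report any adverse experiences that may arise" immediately.

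**How it is reported.** SAP 9.5.1 lists adverse events and counts the individuals affected over the whole study, by arm, system organ class, preferred term and severity. SAP 3.1.1 frames the safety objective over 8 weeks. COWS is not an outcome in SAP 9.2 or a table in Appendix B.

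**Early exit.** Protocol 5.4.2 requires Week 12 procedures at any early exit. Section 7.3.6 requires Week 8 procedures for exits before Week 8 and Week 12 procedures after that. Section 7.2.1 calls for safety labs at Week 12 or the early termination visit.

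**The concern.** A period kept for one safety question should lead to an output that answers it. Here the rating scale is applied on the day the drug stops and again two weeks later, and the by-arm summaries make no cut at the last dose. Withdrawal symptoms also overlap with drug side effects. Section 2.3.1 names nausea, pain and diarrhea among the symptoms to treat after stopping, and it also lists nausea (29% vs 11%) and diarrhea (13% vs 10%) as XR-NTX effects relative to placebo. At stake is whether the trial can say, by arm, what happened when people without opioid dependence stopped this combination.

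The exit rules raise a separate, operational problem. With about 30% attrition expected (Protocol 10.5), sites need one instruction. A site following 7.3.6 for an exit before Week 8 would skip COWS and the full safety labs.

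**Working it through.** **1. Time off drug at the second COWS.** (14 − 12) × 7 = 14 days, which agrees with the two weeks stated in 7.3.7. If the ±7-day window in 7.3.4 also covers Week 14 (not stated), the range is 7 to 21 days.

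**2. Which episodes a day-14 COWS can see.** Let s be the start day after the last dose and d the duration in days. An episode is in progress on day v if s ≤ v ≤ s + d. With v = 14:
- d = 2 requires s = 12 to 14.
- d = 1 requires s = 13 to 14.

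Moving v to 7 or 21 only shifts the 2-day range, to s = 5 to 7 or s = 19 to 21.

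**3. What the phone call adds.** The documents give no onset time, so both cases below are assumptions.
- *Early onset, s = 1 to 3, d = 1 to 2.* The time from end of episode to Week 14 is 14 − (s + d), which is 9 to 12 days. To a call on day 5 it is 5 − (s + d), which is 0 to 3 days. To a call on day 3 it is at most 1 day, or the episode is still in progress. The call suits this case.
- *Delayed onset, d = 2, starting after the call and over before day 14.* With the call on day 3, s = 4 to 11 and the gap to Week 14, 14 − (s + 2), is 1 to 8 days. With the call on day 5, s = 6 to 11 and the gap is 1 to 6 days. This case rests on self-report or on the adverse event enquiry at Week 14.

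**4. Does any planned output isolate post-stop events by arm?**
- SAP 9.5.1: whole study. A person with nausea at Week 2 and again on day 3 after stopping is still one person with nausea.
- SAP 9.2: adverse event comparisons are split by type and severity, not by period.
- SAP Appendix A: the daily proportion with any event is all-cause and is not described by arm or as counted from the stop date.
- Protocol 10.4.4: the hazard analysis is not stated to start at the last dose, and the side effect scales to be compared are not named.

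An event recognized as withdrawal could appear under its own term, since 2.3.1 lists "signs and symptoms of withdrawal" among SL-BUP events. Symptoms recorded singly would not be distinguishable in the summaries.

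**5. Exit before Week 8, the two rules side by side (7.3.1 schedule and footnotes, 7.2.1).**

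| Item | 5.4.2 (Week 12 set) | 7.3.6 (Week 8 set) |
|---|---|---|
| COWS | yes | no |
| CIWA-Ar | yes | no |
| Full safety labs | yes | no (GGT; ALT/AST only if raised at baseline) |
| C-SSRS | no | yes |

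The two rules agree for exits between Weeks 8 and 12.

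**6. What a post-stop summary could state.** If none of n active participants had a withdrawal-type event after the last dose, the exact two-sided 95% upper limit is 1 − 0.025^(1/n).
- n = 45: 7.9%.
- n = 31 (0.70 × 45 = 31.5, rounded down, assuming that dropouts leave no post-stop data): 11.2%.

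These limits show what the summary could say. They do not estimate how much would be missed.

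**The case against.** The strongest reply is that COWS is not the main tool in this interval. Protocol 7.1.1 describes it as an eligibility instrument. Monitoring rests on the nurse call, the telephone contact marked for adverse events between Weeks 12 and 14, dated adverse events, and the Week 14 visit. In the delayed case, recall over 1 to 8 days is ordinary for a trial with two-weekly visits. SAP 9.5.1 also plans an event listing, and Appendix B is a list of potential tables, so a table's absence there does not rule it out. Most of this stands, and it is why the weight is low. What remains is that the SAP does not say the listing will show onset relative to the last dose, and a listing is not a by-arm summary with a denominator.

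A reader might infer that withdrawal would go undetected. The documents do not support that. Capture is in place, no onset time is given, and the 1 to 2 day length comes from higher doses than 2 mg with XR-NTX. A reader might also infer from the 8-week safety objective that post-stop data are discarded. SAP 9.5.1 covers the whole study, so they are not.

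On early exit, 5.3 encourages early leavers to complete Week 12 assessments, which favors 5.4.2. A COWS at exit in someone still taking tablets is only a stop-day reading and adds little there. Both points are fair, but the two sections still give different instructions.

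**Conclusion.** The point holds, with minor to modest weight. After screening, COWS is scored on the stop day and about 14 days later. The by-arm summaries pool post-stop with on-treatment events, so the monitoring period has no by-arm output of its own. The underlying data are mostly collected. No efficacy estimate is affected, the protocol expects withdrawal to be highly unlikely, and the cited cases were mild.

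The conflict between 5.4.2 and 7.3.6 is plain in the text. It is confined to exits before Week 8 and extends to the early-termination labs in 7.2.1.

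The timing results rest on the cited 1 to 2 day duration and on assumed onset days. The incidence of withdrawal on this regimen is unknown.

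**What to change.** 1. **One early-exit rule in 5.4.2 and 7.3.6.** For exits before Week 8, do the Week 8 procedures plus COWS, CIWA-Ar and safety labs. Simply switching 7.3.6 to the Week 12 set would drop the C-SSRS, which is scheduled at Week 8 but not at Week 12.
2. **One by-arm summary in the SAP, specified before unmasking.** Count participants with adverse events starting after the last sublingual tablet (SL-BUP or SL-PLC), through Week 14 or last contact. List the withdrawal-type terms in advance and give the number followed in each arm. The tablet should define the last dose, because the last injection is at Week 8 (SAP 9.2), nominally (12 − 8) × 7 = 28 days before the tablets stop. Onset dates are already collected. Choosing the terms after unmasking would make the summary post hoc.
3. **Optional.** At the existing day 3 to 5 call, ask the COWS symptom items that can be answered by phone.

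The cost is one extra table, a slightly longer call that relies on recall and cannot score items needing observation, and IRB approval of a small amendment for items 1 and 3 (Protocol 13.2). Treatment and clinical care do not change.

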2.3.2 POTENTIAL BENEFITS

Extended-release naltrexone is FDA approved for the treatment of alcohol dependence, as well as for the prevention of relapse to opioid dependence, following opioid detoxification. Thus, naltrexone may directly benefit the participants in this study and help them to reduce or stop the use of alcohol. As described in a report of outcomes from the Vivitrol's Cost and Treatment Outcomes Registry, XR-NTX has been used effectively and safely.¹⁷

As described in the section above, SL-BUP has antidepressant effects and may help attenuate the symptoms of PTSD.

When added to XR-NTX, SL-BUP may further potentiate the anti-craving effects and reduce alcohol use and this combination may reduce symptoms of PTSD. Reducing alcohol use may also be a factor in reduction of PTSD symptoms and conversely, reduced PTSD symptoms may lower the participants' tendency to self-medicate with alcohol.

Another benefit of the study is that knowledge to be gained can help guide treatment for patients with comorbid AUD and PTSD in the future.

